7 ADVERSE EVENTS

7.1 Regulatory Definition of an Adverse Event

In the International Conference on Harmonization (ICH) E6 Guideline for Good Clinical Practice, Section 1.2 defines an adverse event (AE) as any untoward medical occurrence in a patient or clinical investigation subject administered a pharmaceutical product and which does not necessarily have a causal relationship with this treatment. An AE can therefore be any unfavorable and unintended sign (including an abnormal laboratory finding), symptom, or disease temporally associated with the use of a medicinal (investigational) product, whether or not considered related to the medicinal (investigational) product.

7.2 Adverse Event Definition for the Purposes of This Study

For the purposes of this the Sponsor clinical study, adverse events will be defined as follows:

An adverse event (AE) is any untoward medical occurrence in a subject who has signed an informed consent form and is participating in a clinical investigation. An AE can be any unfavorable and unintended sign (including an abnormal laboratory finding), symptom, or disease, whether or not considered related to the study drug (investigational product).

Preexisting events that increase in frequency or severity or change in nature during or as a consequence of participation in clinical studies will also be considered as adverse events. An AE may also include pre- or post-treatment complications that occur as a result of a protocol-mandated procedure (such as a biopsy).

Any medical condition or clinically significant laboratory abnormality with an onset date prior to the time the subject signed the informed consent form is considered to be preexisting and should be documented in the medical history CRF, if applicable for the study.

Whenever possible, the diagnosis (rather than a series of terms related to a diagnosis) should be recorded as the AE term.

An AE does not include the following:

- Medical or surgical procedures (such as surgery, endoscopy, tooth extraction, or transfusion); the condition that leads to the procedure is an adverse event
 - Preexisting diseases or conditions present or detected before signing an informed consent form that do not worsen
-

- Situations where an untoward medical occurrence has not occurred (such as hospitalization for elective surgery or social and/or convenience admissions)
- Overdose of either study drug or concomitant medication without any signs or symptoms, unless the subject is hospitalized for observation

7.3 Assessment of Adverse Events

All AEs will be assessed by the investigator and recorded in the case report form, including the dates of onset and resolution, severity, relationship to study drug, outcome, and action taken with study medication.

Clinical severity should be recorded and graded using mild, moderate or severe as described below.

Mild	= Awareness of signs or symptoms, but easily tolerated
Moderate	= Discomfort sufficient to cause interference with usual activities
Severe	= Incapacitation with inability to work or perform usual activities

The relationship to study drug therapy should be assessed using the following definitions:

- **Not Related:** Evidence exists that the adverse event has an etiology other than the study drug (such as a preexisting condition, underlying disease, intercurrent illness, or concomitant medication).
- **Possibly/Probably Related:** A temporal relationship exists between the event onset and administration of the study drug. It cannot be readily explained by the subject's clinical state or concomitant therapies and appears **with some degree of certainty** to be related based on the known therapeutic and pharmacologic actions of the drug. In case of cessation or reduction of the dose, the event abates or resolves and reappears upon rechallenge. It should be emphasized that ineffective treatment should not be considered as causally related in the context of adverse event reporting.

These criteria in addition to good clinical judgment should be used as a guide for determining the causal assessment. If it is felt that the event is not related to study drug therapy, then an alternative explanation should be provided.

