3.5.2 Treatment Assignment

All subjects will receive a single dose of telavancin. See Section 5.2 for information regarding dose administration.

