
Any occurrence of a suspected telavancin-related severe or serious adverse drug reaction
	
 • Stop dosing additional subjects and convene SDRC (if event occurs outside the regularly scheduled SDRC). • Review AE and all relevant safety data for evidence of relationship to treatment and clinical or medical significance. • If a severe or serious adverse event is determined by the SDRC to be related to study drug and clinically or medically significant, no further administration at this dose should occur. Enrollment of the study may continue at a lower dose upon unanimous decision of the SDRC.

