7.6 Serious Adverse Event Reporting

Any SAE that occurs after a subject signs an informed consent form through the follow-up visit (or at the time a subject is determined to be ineligible for the study or who does not enroll in the study), regardless of causal relationship, must be reported to the Sponsor within 24 hours of the investigator's knowledge of the event.

To report an SAE, complete and fax the Serious Adverse Event Report Form to the following:

[REDACTED]

For medical questions regarding an SAE, contact the Sponsor medical monitor by telephone as follows:

[REDACTED]

For fatal or life-threatening events, also fax copies of hospital case reports, autopsy reports, and other documents when requested. Additional information may be requested from the investigator to ensure the timely completion of accurate safety reports.

An SAE may qualify for reporting to regulatory authorities if the SAE is possibly attributable to the study drug and is unexpected/unlisted based on the current Telavancin Investigator's Brochure. In this case, all investigators will receive notification of the event. The investigator is responsible for notifying the Institutional Review Board or Ethics Committee and documenting the notification, as required by local regulatory authorities and in accordance with the local institutional policy.

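### Section 7.3's only 'related' category includes recurrence on rechallenge, which one dose cannot show, and its two categories leave some post-dose events unclassified, so causality calls may be inconsistent or too low

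*Combined protocol and SAP*

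**What the plan says.** Section 7.3 asks the investigator to place each adverse event in one of two categories.

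- **Not Related**: "Evidence exists that the adverse event has an etiology other than the study drug". Pre-existing condition, underlying disease, intercurrent illness and concomitant medication are the examples.
- **Possibly/Probably Related**: the description opens "A temporal relationship exists between the event onset and administration of the study drug". It continues "It cannot be readily explained by the subject's clinical state or concomitant therapies and appears", followed by a bolded phrase asking for some certainty of relatedness, based on the drug's known actions. It then adds: "In case of cessation or reduction of the dose, the event abates or resolves and reappears upon rechallenge".

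The section closes with a softening sentence, "These criteria in addition to good clinical judgment should be used as a guide for determining the causal assessment", and asks for an alternative explanation whenever an event is felt to be unrelated.

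Section 3.5.2 states: "All subjects will receive a single dose of telavancin". Section 5.2 allows for the infusion being stopped; for red man syndrome it is stopped and not restarted.

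The causality call is used in three places:

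- Section 8.5.5 tabulates treatment-emergent events by relationship.
- Both rows of Table 4 (Section 6.5) turn on suspected relatedness. The second row reads "Any occurrence of a suspected telavancin-related severe or serious adverse drug reaction".
- Section 7.6 says: "An SAE may qualify for reporting to regulatory authorities if the SAE is possibly attributable to the study drug and is unexpected/unlisted".

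**The concern.** One element of the 'related' definition cannot occur under this design, and an investigator who treats it as required has no route to a 'related' call. The remaining elements can be assessed but are demanding in this population. Every child needs, or has just completed, systemic antibiotics for treatment or prevention of infection (Section 4.1). Other antibiotics are allowed (Section 6.6), including vancomycin if no level is needed in the window (Section 4.2). A competing explanation will often be at hand.

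Safety and tolerability are the secondary objective. Table 4 is the written rule that stops dosing between scheduled reviews, while all cohorts enrol in parallel. If sites read Section 7.3 differently, the relationship column becomes hard to interpret in a trial of about 30 children, and the unscheduled triggers depend on which site saw the event.

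**Working it through.** The plan states no related-event rate, classification accuracy or trigger probability, so there is no figure to reproduce. The check is mainly textual.

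**1. Which elements of 'related' can be observed after one dose?**

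| Element in 7.3 | Observable? |
|---|---|
| Temporal relationship | Yes |
| No ready alternative explanation | Yes, by judgment |
| Some certainty from known actions | Yes, by judgment |
| Abatement on cessation or reduction | Only if the infusion is cut short (5.2) |
| Recurrence on rechallenge | No: one dose each (3.5.2) |

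For red man syndrome, the one event for which Section 5.2 itself orders stopping, it also rules out resumption. Abatement could be seen there, but recurrence could not.

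**2. Are the two categories exhaustive?** Take a hypothetical moderate rash a few hours after the infusion in a child also taking another antibiotic, with nothing to show which drug caused it. The timing fits. The co-medication is a ready explanation, so the second element of 'related' fails. Yet no evidence shows that the other drug was the cause, so 'Not Related' fails too. One site may count mere plausibility as evidence and record 'Not Related'; another may not. The text does not settle it.

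**3. Is the threshold the same throughout?**

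| Place | Standard |
|---|---|
| 7.3, category label | possibly or probably |
| 7.3, description | some degree of certainty, from known actions |
| Table 4, both rows | suspected |
| 7.6, regulatory reporting | possibly attributable |

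The description in Section 7.3 sets a higher bar than its own label and than the two rules that use relatedness.

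**4. How sensitive are the Table 4 triggers to under-classification?** This is an illustration only. Let N = 30 (the planned total, Section 3.2), p the true per-subject rate of a qualifying drug-related event, and s the share classed as related. Both p and s are assumptions, and subjects are taken as independent. With q = p × s:

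- at least one event: 1 − (1 − q)^30
- at least two subjects: 1 − (1 − q)^30 − 30q(1 − q)^29

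For example, p = 5% and s = 0.5 give q = 0.025, and 1 − 0.975^30 = 0.532.

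| Trigger | p | s = 1 | s = 0.75 | s = 0.5 | s = 0 |
|---|---|---|---|---|---|
| ≥1 severe or serious | 2% | 0.455 | 0.365 | 0.260 | 0 |
| ≥1 severe or serious | 5% | 0.785 | 0.682 | 0.532 | 0 |
| ≥2 moderate, one system class | 5% | 0.446 | 0.311 | 0.172 | 0 |
| ≥2 moderate, one system class | 10% | 0.816 | 0.669 | 0.446 | 0 |

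The triggers weaken as s falls. They reach zero only at s = 0, which would require rechallenge to be mandatory.

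**The case against.** A reader might infer that no event could ever be classed as related, so that related events and the triggers are biased towards zero. The documents do not support this, for these reasons:

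- The rechallenge sentence is conditional, and it follows three elements that can be judged after one dose. The criteria are a guide used with clinical judgment, not a checklist.
- The wording does not all push one way. 'Not Related' needs evidence of another cause, and such a call should carry an alternative explanation. Both pull unclear events away from 'Not Related', so the direction of misclassification is not established.
- Section 1.4 lists single-dose effects, such as taste disturbance and foamy urine, that an infection does not obviously explain. It goes too far to say that almost every event has a ready alternative.

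A reader might also infer that the known-actions clause contradicts the unexpectedness test in Section 7.6. It does not. Unlistedness is judged against the Investigator's Brochure, and an event can be pharmacologically plausible and still unlisted. What remains is the difference in threshold.

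Some safeguards do not depend on Section 7.3. All SAEs reach the Sponsor within 24 hours whatever their cause. Scheduled Safety Data Review Committee meetings see all available safety data, and the committee judges relationship itself once convened. Treatment-emergent events are also tabulated by class, term and severity, and all individual data are listed.

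These points stand, but the safeguards are partial. SAE reporting does not cover moderate or severe non-serious events. Scheduled reviews come only after about every 8 subjects (about 6 in Cohort 4). The committee is internal to the Sponsor, and a 'Not Related' call does not itself convene it.

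**Conclusion.** The point holds as a defect of definition that should be corrected. It is not a demonstrated bias. Three things are established from the text: recurrence on rechallenge cannot be observed in any of the roughly 30 subjects, some post-dose events fit neither category, and Section 7.3 sets a stricter threshold than Table 4 and Section 7.6. Together they create a risk of under-attributed and inconsistent causality calls, affecting the table by relationship and the unscheduled Table 4 triggers.

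The size of the effect is unknown because the documents give no value for the share of drug-related events classed as related. The probabilities above show sensitivity under assumed rates and predict nothing about this trial. An event missed as a trigger would still come to the next scheduled review, so the loss is mainly one of timeliness. The primary PK objective is not affected.

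**What to change.** Rewrite the causality paragraph in Section 7.3:

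1. Delete the cessation and rechallenge sentence. Alternatively, state that abatement on stopping the infusion is supportive only, and that its absence does not argue against relatedness.
2. Make known pharmacology supportive and not a condition.
3. Use one deciding question for every post-dose event: is there a reasonable suspicion that telavancin contributed? If yes, the event is Possibly/Probably Related. 'Not Related' is kept for events where evidence of another cause, recorded by the investigator, leaves no such suspicion. Each post-dose event then falls into exactly one category.
4. Class events with onset before the infusion as not related. Assess a condition that worsens after dosing as a post-dose event, in line with Section 6.4.3.2.
5. Align the relatedness wording of Section 7.3 with Table 4 and Section 7.6, leaving the stopping actions as they are.

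It would go too far to class as related every post-infusion event without proof of another cause. With Table 4 unchanged, a single severe or serious event of uncertain origin would then pause dosing, and that would alter in practice how the stopping rule operates. The reasonable-suspicion test avoids this.

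The cost is one paragraph in an amendment and matching CRF guidance. Somewhat more events may be classed as related, so Table 4's pause in dosing and committee review may be triggered more often.

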7.4 Serious Adverse Events

A serious adverse event (SAE) is defined as any adverse drug experience occurring at any dose that results in any of the following outcomes:

- Death
 - Life-threatening situation (subject is at immediate risk of death)
-

- Inpatient hospitalization or prolongation of existing hospitalization (excluding those for study therapy or placement of an indwelling catheter, unless associated with other serious events)
- Congenital anomaly/birth defect in the offspring of a subject who received study drug
- Other: Important medical events that may not result in death, be immediately life-threatening, or require hospitalization, may be considered an SAE when, based upon appropriate medical judgment, they may jeopardize the subject and may require medical or surgical intervention to prevent one of the outcomes listed in this definition. Examples of such events are as follows:
 - Intensive treatment in an emergency room or at home for allergic bronchospasm
 - Blood dyscrasias or convulsions that do not result in hospitalization
 - Development of drug dependency or drug abuse

Additional Considerations for Serious Adverse Events

- Death is an outcome of an adverse event and not an adverse event in itself. In reports of death due to disease progression, where no other information is provided, the death will be assumed to have resulted from progression of the disease being treated with the study drug(s).
- All deaths, regardless of cause, must be reported for subjects if the death occurs while the subject is participating in the study.
- “Occurring at any dose” does not imply that the subject is receiving study drug at the time of the event; dosing may have been given as treatment cycles or interrupted temporarily before the onset of the SAE, but may have contributed to the event.
- “Life-threatening” means that the subject was at immediate risk of death from the event as it occurred. This does not include an event that might have led to death, if it had occurred with greater severity.
- Complications that occur during hospitalizations are AEs. If a complication prolongs hospitalization, it is an SAE.
- “Inpatient hospitalization” means the subject has been formally admitted to a hospital for medical reasons, for any length of time. This may or may not be overnight. It does not include presentation and care within an emergency department.
- The investigator should attempt to establish a diagnosis of the event based on signs, symptoms, and/or other clinical information. In such cases, the diagnosis should be documented as the AE and/or SAE and not the individual signs/symptoms.

7.5 Clinical Laboratory Abnormalities and Other Abnormal Assessments as Adverse Events or Serious Adverse Events

Abnormal laboratory findings (such as clinical chemistry, hematology, or urinalysis) or other abnormal assessments (such as electrocardiograms [ECGs], X-rays, or vital signs) that are associated with signs and/or symptoms or are considered clinically significant in the judgment of the investigator must be recorded as AEs or SAEs if they meet the definition of

an adverse event (or serious adverse event), as described in Sections 7.2 (Adverse Event Definition for the Purposes of This Study) and 7.4 (Serious Adverse Events).

If there are any AE questions, the investigator is encouraged to contact the Sponsor clinical study director or medical monitor to discuss.

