1.4 Risks and Benefits

The efficacy of telavancin has been demonstrated in Phase 3 studies of adult patients suspected to be caused by Gram-positive bacterial pathogens, in which telavancin demonstrated noninferiority to vancomycin. Because the current study will be evaluating single doses of telavancin in this pediatric population, no benefits are anticipated.

In single-dose studies of telavancin, the following adverse events have been reported: taste disturbance, headache, pruritus/urticaria, flushing, red man syndrome, hypersensitivity, constipation, transient elevated coagulation parameters, injection site pain, nausea, foamy urine, fatigue, somnolence, vasovagal syncope, decreased serum potassium, increased serum lactic dehydrogenase, and QT prolongation.

In Phase 2 and Phase 3 studies in which multiple doses of telavancin were administered, the following adverse events were reported: infusion-related reactions, urticaria, rash, pruritus, dermatitis, red man syndrome, renal insufficiency, QTc prolongation, ototoxicity, superinfection, and antibiotic-associated colitis/ pseudomembranous colitis. Laboratory abnormalities included elevations in serum creatinine and urea. In addition, increases in alanine aminotransferase (ALT) and aspartate aminotransferase (AST) were observed infrequently with no evidence of a relationship to telavancin dose.

Telavancin may pose a risk to fetuses, based on nonclinical data, and should be avoided during pregnancy unless the potential benefit outweighs the potential risks.

C. difficile-associated colitis is a potential adverse reaction and should be considered in subjects with diarrhea subsequent to drug administration.

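### The SAE definition omits disability or incapacity, so a lasting deficit without hospitalization or threat to life is an SAE, and reportable within 24 hours, only by investigator judgment

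*Combined protocol and SAP*

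**What the plan says.** Section 7.4 opens with a closed list: "A serious adverse event (SAE) is defined as any adverse drug experience occurring at any dose that results in any of the following outcomes". The list has five entries:

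- death;
- a life-threatening situation;
- "Inpatient hospitalization or prolongation of existing hospitalization";
- "Congenital anomaly/birth defect in the offspring of a subject who received study drug";
- other important medical events. These may be treated as SAEs on medical judgment when "they may jeopardize the subject and may require medical or surgical intervention to prevent one of the outcomes listed in this definition". The three examples are allergic bronchospasm treated intensively outside the ward, blood dyscrasias or convulsions without admission, and drug dependency or abuse.

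Three later rules depend on that classification, wholly or in part:

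- Section 7.6: an SAE, "regardless of causal relationship, must be reported to the Sponsor within 24 hours" of the investigator learning of it. Possible onward reporting to regulators, with notice to all investigators, is also written for SAEs.
- Section 6.5, Table 4, second row: dosing of further subjects stops and the SDRC convenes on "Any occurrence of a suspected telavancin-related severe or serious adverse drug reaction".
- Section 8.5.5: serious TEAEs are summarized separately.

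Section 1.4 names, among events from multiple-dose Phase 2 and 3 studies, "red man syndrome, renal insufficiency, QTc prolongation, ototoxicity, superinfection". Its separate list of events from single-dose studies does not include ototoxicity.

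**The concern.** Lasting disability or incapacity is a serious result in its own right, yet it is not among the listed outcomes and no other section makes it a seriousness criterion. The idea of incapacity appears only in the Section 7.3 severity scale, and a severity grade does not make an event an SAE.

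The catch-all does not clearly fill the gap. It points to outcomes already on the list, so an event whose harm is the deficit itself, such as permanent partial hearing loss, has no listed outcome to attach to.

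The stake is how quickly and how surely the sponsor learns of such an event in a child. Section 1.4 expects no benefit to subjects from the single dose, and Section 8.6 plans no monitoring committee independent of the sponsor. Oversight therefore leans on correct classification by the investigator.

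**Working it through.** No arithmetic applies: the plan gives no figure on this point. The check follows one type of event through the rules.

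**Event considered.** A lasting deficit after the dose, with no admission, no prolonged stay and no immediate risk of death.

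**Step 1: is it an SAE under Section 7.4?** By construction, the death, life-threatening and hospitalization entries do not apply, and congenital anomaly is not relevant. Only the important-medical-event entry remains. It is permissive, rests on judgment, and is framed around preventing an outcome on the list. Disability is not on the list. SAE status is therefore possible but not required.

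**Step 2: which severity grade can it carry under Section 7.3?** Severe means the subject is incapacitated and cannot carry on normal activity. Moderate means discomfort enough to interfere with normal activity. A permanent but partial deficit can fit moderate.

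**Step 3: what follows?**

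| Classification of the deficit | 24-hour report (7.6) | Serious-TEAE summary (8.5.5) | Table 4 stop |
|---|---|---|---|
| Classed as SAE by judgment, suspected related | Yes | Yes | Yes, second row, one case |
| Not SAE, related, severe | No | No | Yes, second row, one case |
| Not SAE, related, moderate, two or more subjects in the same system class | No | No | Yes, first row |
| Not SAE, related, moderate, one subject | No | No | No |
| Not SAE, not related, any grade | No | No | No |

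The first row of Table 4 excepts red man syndrome and local site reactions, which does not affect this example.

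**Step 4: where does the omission change the result?** Compare the first and fourth lines. The same single moderate deficit stops dosing if it is called serious and triggers nothing if it is not. In the second line the stop applies, but Section 7 sets no deadline for telling the sponsor about a severe, non-serious reaction. It goes into the case report form (7.3), and contact over AE questions is encouraged (7.5). Meanwhile all four cohorts enroll in parallel at about 10 sites, and routine SDRC meetings come after roughly 8 subjects for Cohorts 1-3 and 6 for Cohort 4.

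**Step 5: is the list complete as read?** It runs over a page break between the life-threatening and hospitalization entries. No redaction or gap is marked there, so I take it as complete. The source page deserves a glance.

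**The case against.** The strongest reply is that the plan has other ways to catch such an event, and much of that is right.

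- **Other routes to seriousness.** A reader might infer that a permanent deficit meets no seriousness criterion at all. The documents do not support that. Prolonged hospitalization counts, and it is a realistic route in subjects who need or have just finished systemic antibiotics and whose Day 2 is headed as the day of discharge. The important-medical-event entry is also open to judgment. Its drug-dependency example is not obviously tied to preventing a listed outcome, which suggests that a broader reading was intended. This makes SAE status possible, but still not required.
- **The stopping rules.** A reader might infer that a disabling reaction escapes Table 4. It does not if it is suspected related and graded severe, because the second row fires on severity or seriousness. The first row adds repeated moderate reactions. What remains is a related deficit graded below severe and not repeated at moderate grade in the same system class.
- **Ototoxicity.** A reader might infer that hearing loss is an expected event here. Section 1.4 lists ototoxicity only from multiple-dose studies, and this trial gives one dose. It illustrates the gap and says nothing about frequency.
- **Ordinary AE handling.** Every AE is recorded with severity, relationship and outcome, followed to resolution or stability (7.7), reviewed by the SDRC, and tabulated by severity and relationship (8.5.5). The event would not vanish. None of this, however, sets a 24-hour clock or puts the event in the serious-TEAE summary.
- **Regulatory duties.** Section 9.1 binds the investigator to report under 21 CFR 312.64. The protocol does not reproduce that rule or any deadline from it, so I give it no weight either way.

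**Conclusion.** The point holds in a limited form. Section 7.4 omits persistent or significant disability or incapacity, and the only remaining entry is discretionary and refers back to the incomplete list. For a lasting deficit without hospitalization or threat to life, the 24-hour report and inclusion in the serious-TEAE summary depend on investigator judgment. Table 4 is weakened only for a related deficit that is graded below severe, is not classed as serious, and does not meet the repeated-moderate rule.

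The size is a class of events, not a rate: the documents give no frequency for such deficits after a single dose. The primary PK analysis is unaffected. The conclusion assumes that the list is complete as printed and that investigators apply Section 7.4 as written. An investigator who reads the important-medical-event entry broadly would report the event, but the protocol should not rely on that.

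**What to change.** Add *Persistent or significant disability or incapacity* as a listed outcome in Section 7.4 and carry it into the SAE report form. The addition does two things. It makes such an event an SAE by rule, so Sections 7.6 and 8.5.5 apply without further edits. It also brings disability within the important-medical-event entry, which would then cover events that may need intervention to prevent it. Table 4 needs no rewording on this account.

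The cost is one line in a protocol amendment, one line in the form, and a note to sites. It adds no visits, samples or procedures.
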